6.2.1.2 Adverse Event Relatedness

The Principal Investigator (Investigator) will make a judgment regarding whether or not, in his/her opinion, the AE was related to study drug. However, even if the Investigator feels there is no relationship to the study drug, the AE MUST be recorded on the adverse event eCRF. Below are guidelines for relationship assessment:

Causality of Adverse Event:

The Causality of Adverse Events refers to the relationship of the AE to study drug. Causality will be categorized according to the following criteria:

Not related:	Adverse events for which a reasonable explanation for an alternative cause is considered plausible, e.g., no study drug taken, plausible clinical alternative like accidental injury, expected progression of underlying or concomitant disease, pharmacologically incompatible temporal relationship, or intercurrent illness.
Related:	Adverse events for which a reasonably possible clinical and/or pharmacological relationship to study drug cannot be excluded, e.g., lacking plausible alternatives.

6.2.2 Serious Adverse Events

Serious adverse events will be reportable from the time the patient signs the ICF through their last study visit (e.g. Visit 6 or Visit 12) or until the Investigator in collaboration with IntraBio Ltd determines that follow-up is no longer necessary. Serious adverse events that are suspected to be drug related will be reported even if they occur up to 30 days after the patient has taken the last dose of study drug. If a related SAE is ongoing at the end of the study or when a patient withdraws from the study, appropriate safety follow-up, including additional laboratory tests as required, will continue for 30 days.

A SAE is any AE that results in any of the following outcomes:

- Death
- Life-threatening experience
- Inpatient hospitalization or prolongation of existing hospitalization
- Persistent or significant disability/incapacity
- Congenital anomaly or Birth Defect
- Important medical events that, based upon appropriate medical judgment, may jeopardize the patient and may require medical or surgical intervention to prevent one of the outcomes listed above.

Life-threatening experience. Any adverse experience that places the patient, in the view of the reporter, at immediate risk of death from the adverse experience as it occurred, i.e., does not include an adverse experience that had it occurred in a more severe form, might have caused death.

Required or prolonged inpatient hospitalization. The adverse experience resulted in an initial inpatient hospitalization or prolonged an existing hospitalization of the patient. If a patient is hospitalized as part of the clinical use of the product, a period of normal hospitalization will be outlined in the protocol or by the judgment of the Investigator. Hospitalizations longer than this period will be prolonged hospitalizations.

Persistent or significant disability/incapacity. An adverse experience that resulted in a substantial disruption of a person's ability to conduct normal life functions.

Congenital Anomaly. The exposure of the patient to the drug or biologic during pregnancy that is judged to have resulted in the congenital anomaly/birth defect.

Important medical events. Adverse experiences that may not result in death, be life-threatening, or require hospitalization may be considered a serious adverse experience when, based upon appropriate medical judgment, may jeopardize the patient or subject and may require medical or surgical intervention to prevent 1 of the outcomes listed above. Important medical events or interventions may be considered an SAE based upon medical judgment of the Investigator.

6.2.2.1 Reporting Serious Adverse Events

SAEs will be reported promptly once the Investigator determines that the event meets the protocol definition of an SAE. The Investigator or designate will fill out the SAE reporting

form in the eCRF within 24 hours of his/her becoming aware of these events. In addition, for fatal and life-threatening events, the Sponsor's Medical Monitor should be contacted immediately. Contact numbers for the Medical Monitor (including after-hours cover) will be provided to the site before any patients are screened and upon receipt should be kept in the Site's study binder.

The SAE Reporting Form of the eCRF will always be completed as thoroughly as possible with all available details of the event within the designated time frames. The Investigator will always provide an assessment of causality at the time of the initial report as described in Section 6.2.1.2.

If the Investigator does not have all information regarding an SAE, he/she will not wait to receive additional information before completing the form. The SAE reporting form will be updated when additional information is received within 24 hours of receipt of such information.

The completion of the SAE Reporting Form in the eCRF is the preferred method for Reporting SAEs. Only if a technical failure prevents the ability to report an SAE in the eCRF, then the paper SAE Reporting Form provided by the Sponsor must be completed and

The fax and or email instructions can be found on the paper SAE Reporting Forms, which are filed in the Investigator Site File.

6.2.2.2 Responsibilities of the Sponsor

The Sponsor or their delegate, is responsible for fulfilling all obligations regarding notification of Regulatory Authorities, Independent Ethics Committees (IECs)/ Institutional Review Board (IRBs), and investigators according to applicable regulatory requirements (expedited and periodic reporting, e.g., serious unexpected suspected adverse reactions, Development Safety Update Report).

6.2.3 Pregnancy

Every effort should be made to prevent pregnancy during the study treatment period. All patients of reproductive potential involved in the study are required to use highly effective methods of contraception during the study and for 28 days after the last IB1001 dose. Female patients will be instructed to notify the Investigator immediately if they discover they are pregnant. Pregnancy data during the study will be reported using the SAE reporting process (see Section 6.2.2). Since it will be necessary to collect detailed information on the course of any pregnancy occurring in a patient on study the Investigator will be provided with the pregnancy notification forms and specific guidance for completing these forms once the initial AE form documenting a pregnancy is received within 24 hours.

Pregnant patients will discontinue study medication for the duration of the pregnancy. The pregnancy will be followed by the Investigator and the outcome of the pregnancy will be reported to the Pharmacovigilance group.

At Visit 2, Visit 4, Visit 6, and then Early Termination Visit (if applicable), females of childbearing potential will have a urine dipstick pregnancy test (analyzed on site).

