From an efficacy point of view, compassionate use of the racemate suggests N-Acetyl-L-Leucine may improve ataxia and quality of life in patients with GM2 [Kaya et al, 2020a]. Preclinical studies have demonstrated that N-Acetyl-L-Leucine is the active ingredient that medications the long-term, neuroprotective, diseases modifying effect of the racemate, while the D-enantiomer is inactive or potentially antagonistic [Kaya et al, 2020b].

Appropriate patient selection is one factor in considering the balance of risks of adverse events (AEs) against potential clinical benefit. The protocol inclusion and exclusion criteria appropriately consider the patient's overall health and medical history.

Based upon the very good safety profile of N-Acetyl-L-Leucine (and N-Acetyl-DL-Leucine) observed in animals at dose levels up to the limit dose (**Description**) as well as knowledge of safe use of N-Acetyl-DL-Leucine in children as young as 9 months of age [Picone, 2018], inclusion of children aged 6 years and over is judged to be safe. Women of childbearing potential and partners of women of childbearing potential will be required to adhere to strict precautions to prevent pregnancy. Women who are pregnant, breast-feeding, or

planning to become pregnant will be excluded from the study. In addition, a negative pregnancy test will be a prerequisite for the inclusion of women of childbearing potential and urine pregnancy tests will be carried out at approximately 6-weekly intervals throughout the trial.

Levels of risk and burden on participants

٦.

N-Acetyl-L-Leucine is being developed for the treatment of adults and children with GM2, a rare and life-threatening disorder that predominantly affects pediatric patients [Utz et al, 2017]. As described above, first evidence of efficacy comes from the long-term compassionate use of N-Acetyl-DL-Leucine in patients with GM2, suggesting the prospect of a direct benefit to the participating patients over standard of care.

To ensure the feasibi	lity of this trial, GM2 clinical experts [
] and the heads of multinational GM2 patient
organizations [
·, 1 ·	were consulted and involved in

its design.

The degree of burden to participants in the study is defined by the description of assessments in Section 7.

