4.1 Inclusion Criteria

Individuals who meet all of the following criteria are eligible to participate in the study:

- 1. Written informed consent signed by the patient and/or their legal representative/ parent/impartial witness
 - a) Male or female aged ≥6 years in Europe OR ≥18 years in the United States with a confirmed diagnosis of GM2 Gangliosidosis at the time of signing informed consent. Confirmed diagnosis, i.e., clinical features and positive genetic test GM2gangliosidosis caused by β-hexosaminidase deficiency resulting from mutations in the HEXA or HEXB genes
- 2. Females of childbearing potential, defined as a premenopausal female capable of becoming pregnant, will be included if they are either sexually inactive (sexually abstinent⁶ for 14 days prior to the first dose and confirm to continue through 28 days after the last dose) or using one of the following highly effective contraceptives (i.e. results in <1% failure rate when used consistently and correctly) 14 days prior to the first dose continuing through 28 days after the last dose:
 - a) intrauterine device (IUD);
 - b) surgical sterilization of the partner (vasectomy for 6 months minimum);
 - c) combined (estrogen or progestogen containing) hormonal contraception associated with the inhibition of ovulation (either oral, intravaginal, or transdermal);
 - d) progestogen only hormonal contraception associated with the inhibition of ovulation (either oral, injectable, or implantable);
 - e) intrauterine hormone releasing system (IUS);
 - f) bilateral tubal occlusion.
- 3. Females of non-childbearing potential must have undergone one of the following sterilization procedures at least 6 months prior to the first dose:

⁶ Sexual abstinence is considered a highly effective method only if defined as refraining from heterosexual intercourse during the entire period of risk associated with the study treatments. In this trial abstinence is only acceptable if in line with the patient's preferred and usual lifestyle.

Periodic abstinence (calendar, symptothermal, post-ovulation methods), withdrawal (coitus interruptus), spermicides only, and lactational amenorrhoea method (LAM) are not acceptable methods of contraception. As well, female condom and male condom should not be used together.

- a) hysteroscopic sterilization;
- b) bilateral tubal ligation or bilateral salpingectomy;
- c) hysterectomy;
- d) bilateral oophorectomy;

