OR be postmenopausal with amenorrhea for at least 1 year prior to the first dose and follicle stimulating hormone (FSH) serum levels consistent with postmenopausal status. FSH analysis for postmenopausal women will be done at screening. FSH levels should be in the postmenopausal range as determined by the central laboratory.

- 4. Non-vasectomized male patient agrees to use a condom with spermicide or abstain from sexual intercourse during the study until 90 days beyond the last dose of study medication and the female partner agrees to comply with inclusion criteria 3 or 4. For a vasectomized male who has had his vasectomy 6 months or more prior to study start, it is required that they use a condom during sexual intercourse. A male who has been vasectomized less than 6 months prior to study start must follow the same restrictions as a non-vasectomized male.
- 5. If male, patient agrees not to donate sperm from the first dose until 90 days after their last dose.
- 6. Patients must fall within:
 - a) A SARA score of $5 \le X \le 33$ points (out of 40)

AND

- b) Either:
 - i. Within the 2-7 range (0-8 range) of the Gait subtest of the SARA scale

OR

- ii. Be able to perform the 9-Hole Peg Test with Dominant Hand (9HPT-D) (SCAFI subtest) in $20 \le X \le 150$ seconds.
- 7. Weight ≥ 15 kg at screening.
- 8. Patients are willing to disclose their existing medications/therapies for (the symptoms) of GM2 Gangliosidosis, including those on the prohibited medication list. Non-prohibited medications/therapies (e.g. concomitant speech therapy, and physiotherapy) are permitted provided:
 - a) The Investigator does not believe the medication/therapy will interfere with the study protocol/results
 - b) Patients have been on a stable dose/duration and type of therapy for at least 42 days before **Visit 1** (Baseline 1)
 - c) Patients are willing to maintain a stable dose/do not change their therapy throughout the duration of the study.

9. An understanding of the implications of study participation, provided in the written patient information and informed consent by patients or their legal representative/parent, and demonstrates a willingness to comply with instructions and attend required study visits (for children this criterion will also be assessed in parents or appointed guardians).

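### Section 6.2.3 gives all patients of reproductive potential one 28-day post-dose contraception period, shorter than the 90 days that inclusion criterion 4 requires of non-vasectomized and recently vasectomized men

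*Protocol*

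**What the plan says.** Section 6.2.3 (Pregnancy) states a single rule without distinguishing the sexes. It is addressed to every patient of reproductive potential and asks for "highly effective methods of contraception during the study and for 28 days after the last IB1001 dose".

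Section 4.1 sets separate rules by sex, and the synopsis repeats them:

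- Criterion 2, for females of childbearing potential who are not abstinent, requires a listed highly effective method "14 days prior to the first dose continuing through 28 days after the last dose". Abstinent women have the same 28-day end point.
- Criterion 4, for non-vasectomized men, requires a condom with spermicide, or that they "abstain from sexual intercourse during the study until 90 days beyond the last dose of study medication".
- Criterion 4 continues: "A male who has been vasectomized less than 6 months prior to study start must follow the same restrictions as a non-vasectomized male".
- For a man with a "vasectomy 6 months or more prior to study start, it is required that they use a condom during sexual intercourse", criterion 4 gives no post-dose period.
- Criterion 5 also uses 90 days: the male "patient agrees not to donate sperm from the first dose until 90 days after their last dose".

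For the Extension Phase, Appendix 6, Section 6.4.3 makes the pregnancy policies the same as Parent Study Section 6.2.3, apart from the timing of pregnancy tests. The Extension inclusion list (Appendix 6, Section 4.1) has no contraception item. Appendix 6, Section 1.1 says that precautions continue but gives no period.

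**The concern.** Two periods are printed for the same men. Eligibility criteria are checked at entry, whereas a post-dose period is applied when a patient leaves. Staff advising a man at that point may well turn to the section headed Pregnancy and find 28 days. In the Extension Phase it is the only section that Appendix 6, Section 6.4.3 names. A site working from that section alone would release these men from precautions well before the 90 days to which they agreed at enrolment. What is at stake is protection against pregnancy in partners. No efficacy or safety analysis depends on it.

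**Working it through.** Section 6.2.3 states a rule, so there is no calculated figure to reproduce. The check sets the rules side by side and then subtracts durations.

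| Group | Section 4.1 | Section 6.2.3 | Difference in stated post-dose period |
|---|---|---|---|
| Females of childbearing potential | 28 days (criterion 2) | 28 days | 28 − 28 = 0 |
| Non-vasectomized men | 90 days (criterion 4) | 28 days | 90 − 28 = 62 |
| Men vasectomized less than 6 months before study start | 90 days (criterion 4) | 28 days | 90 − 28 = 62 |
| Men vasectomized 6 months or more before study start | condom, no post-dose period | 28 days | no shortfall |

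**Are men in scope of Section 6.2.3?** Yes, as written. The section refers to female patients, or to females of childbearing potential, where it means women only. Its contraception sentence refers to all patients. Section 1.1 supports this: "Women of childbearing potential and partners of women of childbearing potential will be required to adhere to strict precautions to prevent pregnancy".

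**Practical shortfall.** Section 6.2.3 requires contraception both during the study and for 28 days after the last dose. Read alone, its obligation ends at the later of leaving the study and day 28 after the last dose. The shortfall is 90 days minus that end point.

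- *Parent Study completer who does not continue.* Section 3.1.2.3 sets a washout of 42 days (+7 days), so Visit 6 falls 42 to 49 days after the last dose. Both exceed 28, so time on study governs. Shortfall: 90 − 42 = 48 days, down to 90 − 49 = 41 days. A postponed Visit 6 (Section 3.1.2.5) reduces it further.
- *Early termination.* Section 4.3 prefers the termination visit 7 to 14 days after the last dose. That is before day 28, so the 28-day period governs. Shortfall: 90 − 28 = 62 days. It is smaller for a man who stops the drug but stays on study beyond day 28.
- *Visit 12.* Dosing in Treatment Period II runs up to this final visit, and SAP Section 6.7 defines no washout cycle for Extension phase II. The 28-day period governs again. Shortfall: 90 − 28 = 62 days.

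**Method.** The two texts also differ here. Section 6.2.3 requires highly effective methods, which criterion 2 defines by a failure rate below 1% and a list. Criterion 4 asks men for a condom with spermicide or abstinence, and a condom with spermicide is not on that list. Changing 28 to 90 in Section 6.2.3 would therefore leave a conflict for men.

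**The case against.** The strongest reply is that the matter is already settled elsewhere. A man enters only if he agrees to criterion 4, and Section 11.3 requires the protocol to be followed exactly. A site that applies the longer period satisfies both texts. Section 6.2.3 can also be taken as the women's rule loosely worded, since it sits under Pregnancy and uses criterion 2's term for methods. The first part stands: criterion 4 is binding, and a shortfall requires a site to overlook it. The second part does not remove the inconsistency, because the sentence covers all patients while its neighbours name females.

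A reader might infer something stronger, that men in the Extension Phase have no 90-day obligation at all because Appendix 6 restates none. The documents do not support that. Every Extension patient must have completed Visit 6 of the Parent Study, so each man to whom the rule applies had already agreed to 90 days. Criterion 4 counts from the last dose of study medication, without limiting this to the Parent Study. Appendix 6, Section 3.3 treats Parent Study and Extension Phase as one study, and Appendix 6, Section 1.1 says that precautions continue.

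Nor can it be inferred that men are told the wrong period. The consent form is not in the text available, so what it says on this is unknown.

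**Conclusion.** The inconsistency is real but minor. Section 6.2.3 is wrong as written for two groups of men, and Appendix 6, Section 6.4.3 sends Extension sites to it. The 41 to 48 days and the 62-day maximum rest on three assumptions: the site relies on Section 6.2.3 alone, the obligation during the study ends at the patient's last visit, and, for Visit 12, criterion 4's 90 days carries into the Extension Phase, which is the reasonable reading. At any site that applies criterion 4 the shortfall is zero. It would go too far to say that all men are affected, since criterion 4 sets no post-dose period for men vasectomized 6 months or more before study start.

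**What to change.** Replace the contraception sentence in Section 6.2.3 with a cross-reference, for example:

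> Patients must follow the contraception methods and durations in the inclusion criteria for their sex (females of childbearing potential: through 28 days after the last dose; non-vasectomized males and males vasectomized less than 6 months before study start: condom with spermicide or abstinence until 90 days after the last dose), in both the Parent Study and the Extension Phase.

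This settles period and method together and adds no new obligation for men vasectomized 6 months or more before study start. Appendix 6, Section 6.4.3 then inherits the correction through its existing reference. The cost is one sentence at the next amendment, with no change to visits, data collection or analysis.

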6.2.4 Vital Signs

Vital signs will be measured and recorded at the time points designated on the schedule of events (Appendix 3A for "naïve" patients and Appendix 3B for "non-naïve" patients). The

following measurements must be performed: systolic/diastolic blood pressure and pulse. Vital signs will be measured after the subject has been in the supine position for at least 5 minutes. All measurements will be recorded on the vital signs eCRF. Abnormal test results may be repeated at the discretion of the Investigator and must be reported on the corresponding eCRF.

Due to COVID-19, vital signs may not be able to be collected at the designated timepoints in the schedule of events (e.g. if visits are skipped and replaced by a remote visit or postponed). The Sponsor's Medical Expert, Medical Monitor, and DSMB deem the risk posed by vital signs not being collected at the designated timepoints due to COVID-19 is acceptable in the context of remote visits where study staff will enquire regarding the health and wellbeing of the patient and assess for adverse events. This decision was based on the nature of the drug, the available non-clinical and clinical data for N-Acetyl-L-Leucine and N-Acetyl-DL-Leucine (see Section 1), and the safety profile observed to date in this ongoing, open-label study (very well-tolerated) (and also in other ongoing trials with IB1001).

6.2.5 Electrocardiograms (ECGs)

During the study, 12-lead ECGs will be performed approximately at the time points designated on the schedule of events (Appendix 3A for "naïve" patients and Appendix 3B for "non-naïve" patients). In addition, ECGs may be performed at other visits at the discretion of the Investigator if the findings from a previous ECG was clinically relevant.

The patient must be in a supine position in a rested and calm state for at least 5 minutes before ECG assessment is conducted. If the patient is unable to be in the supine position, the patient should be in the most recumbent position possible.

All ECGs should be performed in a standardized method prior to blood draws or other invasive procedures.

Each ECG must include the following measurements:

Corrected QT, and whether the ECG is Normal, Abnormal NCS (not clinically significant), or Abnormal CS (clinically significant) for the patient.

The Principal Investigator or designated site physician will review and sign all ECGs. Results must be summarized in writing and classified as normal; Abnormal NCS (not clinically significant), or Abnormal CS (clinically significant) for the patient. Intervals of the ECG will be recorded in the eCRF. Once signed, the original ECG tracing will be retained with the patient's source documents. At the request of the Sponsor, a copy of the original ECG will be made available.

Due to COVID-19, ECGs may not be able to be collected at the designated timepoints in the schedule of events (e.g. if visits are skipped and replaced by remote visits or postponed) or if qualified study team members/ appropriate equipment are not available/accessible. The Sponsor's Medical Expert, Medical Monitor, and DSMB deem the risk posed by ECGs not being collected at the designated timepoints is acceptable in the context of remote visits where study staff will enquire regarding the health and wellbeing of the patient and assess for adverse events. This decision was based on the nature of the drug, the available non-clinical and clinical data for N-Acetyl-L-Leucine and N-Acetyl-DL-Leucine (see Section 1), and the safety profile (no reports of cardiac issues, including QTc prolongation) observed in this ongoing, open-label study (and also in other ongoing trials with IB1001). ECGs will be routinely collected at Visit 9 in the Extension Phase, allowing for further assessment of any cardiac effects.

